### **Informed consent procedures**

The Principal Investigator (or their delegate), on the basis of the inclusion and exclusion criteria of the study, identifies the eligible patients. The Principal Investigator (or their delegate) then informs the patient of the study in progress explaining in a clear and simple way the fundamental characteristics of the device, the expected effect, any risks associated with the trial, and briefly explains the characteristics of the device, the expected effect, the possible trial-related risk, the guarantees to protect the confidentiality of the collected information, and asks if the patient is interested in participating, leaving them at least 24 hours to decide. During this interview, the investigator verifies the understanding by the patient or their legal tutor of the information provided. If the patient manifests their interest to participate in the study, they, or if the subject is unable to provide informed consent, their legal representative, signs the Informed Consent and decides whether to inform their attending physician of their participation in the study. At the same time, the patient gives his availability, after any discharge, to return to the facility for the established observation time and for the assessment of the progress of healing and scarring. A copy of the Informed Consent, subscribed by the patient and by the Principal Investigator and a copy of the study information will be given to the patients.

The informed consent shows the title of the investigation, the code and date of the protocol, the sponsor and the main investigator; the objectives and characteristics of the study, the investigations to which the patient will be subjected and the consequences of their participation are described below; the benefits and risks deriving from the trial, the insurance coverage, the possible alternatives, the contact details of the main investigator, the procedures envisaged at the end of the study, the possibility of informing the family doctor are then described. Finally, information on the processing of personal data is set out.

Any news about the trial and/or the medical device under investigation and any eventual amendment to the protocol of clinical investigation will be notified to the patients as soon as the Principal Investigator receives any of them.

If the subject is unable to write, consent can be provided and recorded using suitable alternative means, if there is at least one impartial witness. In this case the witness affixes their signature and the date on the informed consent. The subject, or, if the subject is unable to provide informed consent, their legal representative, receives a copy of the documentation or registration.

### **Pre-clinical tests and previous clinical experience**

#### *Preclinical animal model study observations*

Preclinical observations aimed to characterize safety and efficacy of the Emoled medical device have been preventively performed on murine models. On each anesthetized animal, two wounds (1 cm diameter) were inflicted using an abrasive method. The 30-seconds treatment with Emoled device has been performed on one of the two wounds, then both were/have been medicated to avoid the development of infections. After the treatment, animals have been placed in individual, thermostat cages, until they fully came out from anesthesia.

The observations reported below were extrapolated from tests performed on biopsies taken at specific time points: after the treatment, each animal was observed over a given follow-up period before being sacrificed, and the areas under study were collected and embedded in a compound suitable for cryosectioning (frozen section). They were later used both for histological and immunohistochemical analyses. A large number of observations were collected and they are reported below by making reference to the observed phenomenon.

Inflammatory infiltrate: based on the data obtained 0, 1, 3, 6, 9, 12, 18 and 24 hours after inflicting the wound, it is noted that within the first few hours the amount of inflammatory infiltrate in the areas treated with the Emoled device is higher compared to the untreated wound. The difference decreases between 9 and 18 hours until, after 24 hours, the situation is reversed and the amount of inflammatory infiltrate in the untreated wound is higher than that in the treated wound.

Mast cells and Mast Cell Degranulation Index: although no particular differences in the number of mast cells were found between the treated and untreated samples, this was not the case when mast cell activation was studied: in fact, potent degranulation was observed in the treated sample at 3 hours, which was not seen in the wound not treated with the Emoled device.

Macrophage populations: observations made 0, 3, 6, 9, 18 and 24 hours after inflicting the wound on the populations of M1 macrophages (proinflammatory) and M2 macrophages (pro-healing) show that the anti-inflammatory phase begins 6 hours after inflicting the wound in animals treated with the Emoled device, whereas it is necessary to wait 18 hours for the inflammatory phase to end with the standard treatment. Moreover, after 18 and 24 hours, both the M1 and M2 populations are comparable in the treated and untreated samples, demonstrating that treatment with the Emoled device does not induce responses other than normal physiological reactions.

Based on these studies, it can be concluded that the Emoled device exerts its effect within the first few hours after wound infliction (and therefore within the first few hours after treatment). Our hypothesis is that treatment with the device exerts its effect early in the inflammatory phase of healing and promotes healing both in terms of time (observable based on the data obtained from the inflammatory infiltrate study) and

quality, evident from the significant mast cell activation, resulting in greater histamine release, causing increased activation of various mediators and cell types that may be involved in the healing process.

#### *In-human acute wound study observations and ulcer case study*

The safety and efficacy clinical validation to obtain the CE marking for the EmoLED device for the treatment of acute surgical wounds is ongoing. In particular, the acute observations, whose detailed results are provided in the attached final Report on the clinical trial, have once again demonstrated the device's safety and efficacy in shortening the healing time of spontaneously healing wounds.

Isolated observations in patients with chronic lesions, of various aetiologies, have shown that the device is capable of unblocking the healing process, thus allowing the wound to progress beyond the inflammatory phase by inducing re-epithelialization and wound closure. Observations made using a thermal camera have also shown that, due to the compromised condition of the tissues surrounding the ulcers, the baseline temperature of the limb is lower than normal and that both during and after treatment with the EmoLED device, the temperature never exceeds 40°C.

### **Information related to the clinical investigation**

#### **Study description**

This clinical study will be a prospective, randomized controlled, double-blind single-center study with the aim of evaluating the clinical efficacy and safety of use of a portable, battery-powered light-emitting device that uses LEDs that emit blue light. The clinical study aims to compare the existing standard treatment for grade IC or IIC neuro-ischemic diabetic foot lesions according to the University of Texas Wound Classification in patients with type I or II diabetes, with a protocol that provides for the administration of the treatment with EmoLED for 20 consecutive weeks in addition to conventional therapy.

Enrolled patients have to be managed in Home Care Nursing Service (by nurses of the "Rete Assistenziale Lesioni Cutanee"), after discharge, twice a week, and have to go to the referral outpatient center participating in the trial once a month for follow-up visits, or in case of adverse events.

#### **Primary and secondary objectives**

As better detailed in the paragraph on statistical analysis, we expect to record, in the observation time, a difference in efficacy of the arm of the patients of the Treated Group (treated with EmoLED for 20 weeks) compared to the Control arm in terms of percentage of wounds healed in 24 continuous weeks (20 weeks of treatment plus 4 additional weeks of observation), but also a difference in healing time, wound surface regression, quality of life, perception of pain, acceptance of therapy, safety of treatment and costs related to the two therapies.

#### **Endpoints**

##### *Study primary endpoint*

The primary endpoint of the study will be the percentage of lesions considered healed (meaning as having a lasting and complete re-epithelialization) in the two groups at the twenty-fourth week of observation.

Healing must be confirmed by the Principal Investigator or their staff during an outpatient visit at the reference center participating in the study; the date of the recovery will in any case be indicated as the one of the first response, if it had occurred before the last visit to the reference center.

#### *Study secondary endpoints*

1. Healing time (in which healing is represented by a lasting and complete re-epithelialization);
2. Reduction of the lesion surface in both arms, during the 20 weeks, measured in absolute terms (square centimeters) and as % of the initial size;
3. Quality of life (QoL), evaluated both with specific questionnaires (EuroQoL-5D) and generic questionnaires (Wound-QoL);
4. Perception of pain measured with a subjective analogue rating scale (VAS);
5. Assessment of the costs related to the two arms in the perspective of the National Health System, NHS (considering only direct health costs) and in the perspective of the Society (considering beyond direct health costs, direct non-health costs and indirect costs);
6. Patient's satisfaction with the EmoLED therapy, assessed by administering specific questionnaires;
7. Appreciation, complexity and usefulness of the EmoLED therapy by the operators assessed through the administration of specific questionnaires;
8. Security of treatment (number of Adverse Events in the two groups);
9. Evaluation of the cost-effectiveness of using EmoLED for the treatment of ulcers.

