### **Study Objectives**

This is a pilot case / control clinical study on a group of outpatients with diabetic foot lesions aiming to verify the efficacy and safety of the Blue light photobiomodulation therapy with Emoled medical device, in addition to standard therapy compared to the standard therapy alone, evaluating the percentage of healed lesions (which have reached complete and lasting re-epithelialization), the assessment of the healing time and reduction of the ulcerated area, the perception of pain and the quality of life of the enrolled patients.

The aim of this study is therefore to determine any differences in outcome between the two considered groups and, in particular, if the therapy of the Emoled group is more effective than the standard therapy in terms of healing rate of lesions, healing time and reduction of the ulcerated area, pain perception and quality of life, and if is at least as safe in terms of occurrence of adverse events. Furthermore, another objective is to assess the economic impact of the two treatment options in the two groups.

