### **Measurable parameters**

Following enrollment and signature of the informed consent, during the first visit / treatment, at the reference outpatient center, the salient data and photographic images of the lesion of each patient will be collected in the appropriate data collection form (see Annex).

During the home visits, twice a week (concomitantly with the dressing change and with the treatment with EmoLED for the Treated Group, respectively), photographic images of the lesion of each patient, some clinical data and the perception of pain through VAS scale will be collected. These variables will be measured at each

visit or until healing. During the visits (to be scheduled at least once every 30 days) carried out at the reference center participating in the trial, the clinical data on the Data Collection Form (see Annex), the photographic images of the lesion of each patient, pain perception using the VAS scale and quality of life data will be collected.

Questionnaires relating to the Quality of Life Section will be administered at the first visit and at the last visit. In particular, standard tools such as the generic questionnaire EQ-5D and the specific questionnaire Wound-QoL will be administered, both available and validated in Italian.

The parameters used that will be found for the definition of the result in the study are:

- Re-epithelialization of the lesion / reduction of the lesion area through data collection form and photographic images of the lesions treated with EmoLED and control lesions (Annexes B, C);
- Intensity of pain perceived by the patient through the VAS scale (Annexes B, C);
- presence of infection (Annexes B, C);
- Level of quality of life perceived by the patient through a questionnaire on the quality of life (EuroQoL and Wound-QoL) (Annexes D, E);
- Appreciation of the therapy (patient) through a specific questionnaire to be filled in by the patient (Annex F);
- Satisfaction, complexity and usefulness of using the device (operator) through a specific questionnaire to be filled in by the operator (Annex G);
- Direct and indirect costs (Annexes H, I);
- Detection of Adverse Events (Annexes B, C).

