#### *Registration of clinical data*

The data related to the evaluation of the study endpoints are acquired, for both groups, during the visits.

The parameters of the Data Collection Form, the questionnaires about quality of life and the questionnaire about the acceptability of the therapy are acquired during the outpatient visit at the reference centre and kept on paper for the clinical trial length, and conserved in both paper and digital form; the pictures of the lesion are acquired and kept in digital form, during the length of the clinical trial and afterwards.

The storage coding follows the patient recruitment code and acquisition timing.

During each visit, a picture of the lesion will be taken and analyzed so that the process of healing can be valued in a quantitative and qualitative way.

At each visit, data on the patient's perception of pain will also be collected.

The Quality of Life related questionnaires will be administered at the first visit and at the last visit, scheduled after 24 weeks, at the reference center. In particular, standard tools such as the generic EQ-5D questionnaire, validated in Italian, will be administered. Similarly, the questionnaire for the patient acceptance of the therapy (generic for both the group treated with EmoLED and the control group) will be administered at the

last visit, scheduled after 24 weeks, or on the date of recovery. The operator satisfaction questionnaire (to be administered exclusively to staff belonging to Home Care) will be administered at the end of the study.

*Data collection form (screening period) (Annex A)*

The collection of data relating to the Clinical Section includes the patient's identification code, date of birth, sex and characteristics of the lesion in question. There is also a space for any concomitant pathologies, any drug therapy (to be registered in terms of active substances). The last section is intended for recording the size of the wound.

*Data collection form (Research Center) (Annex B)*

The collection of data relating to the Clinical Section includes the patient identification code, date of birth, sex and characteristics of the lesion to be collected in the initial phase. There is also a space for any concomitant pathologies, any drug therapy (to be registered in terms of active substances), any notes.

The second part of the form is organized as a matrix where the row represents the measurable parameters for each time of observation (reported in column).

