At each visit the investigator marks with an "X" the chosen value for each parameter and the most suitable description. The investigator will also fill a check list, for each visit, to ensure that the picture of the lesion has been taken, and there will also be a checkbox in case of presence of infection in the wound bed.

Regarding the measurement of the size of the lesions, with "length" and "width" it is meant the longest diameter of the lesion and the largest diameter orthogonal to the first.

There is also a section dedicated to recording any additional visits, the date of recovery and the observation period following the end of the treatment. On the last page there is a table for reporting adverse events that will occur during the trial. In this table must be reported all types of adverse events (even serious). In this table will be reported the date of onset of the event, the type of event (there are already some entries of common adverse events that may occur on the wound or in the perilesional tissue), the solution implemented (additional therapy, hospitalization, etc.), the date of resolution of the event, the way of resolution and correlation of the event with topical therapy or treatment with EmoLED. The onset of any adverse event (even not serious or unrelated) must be reported to the sponsor, as well as included in the table above. In case of suspected or established correlation of the adverse event with treatment with EmoLED, the event will be declared as an "incident" and the principal investigator will be obliged to report it to the competent authorities as described in paragraph "Incidents and their reporting".

*Data collection form (Home Care) (Annex C)*

During the home visit phase by the home care staff, a short data collection form will be filled out (twice a week) where in addition to the patient's identification code and belonging to the Treated or Control group, the same parameters of the data collection form will be annotated weekly for the Experimental Center. On the last page there is a table for reporting adverse events (see Annex B).

*Data collection form on Quality of Life (Annexes D, E)*

At the first visit and at the last visit to the experimental center, the enrolled patient will be given a form for the collection of data on quality of life, in which the subject is asked to answer some questions (about autonomy, pain, daily discomfort, etc.) also related to the presence of the chronic lesion under examination.

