#### *Therapy satisfaction questionnaire (Patient) (Annex F)*

The questionnaire on the patient's satisfaction about the therapy (generic for both the group treated with Emoled and the control group) will be administered at the last visit, scheduled after 24 weeks, or at the control visit 4 weeks from the date of recovery. In this questionnaire, the patient is asked questions aimed at understanding whether the therapy (standard or with the addition of treatment with Emoled) has caused any kind of discomfort or has been well tolerated.

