### **Statistical analysis**

Demographic and clinical data will be presented in tables and graphs in the form of frequencies and percentages for categorical variables, mean, standard deviation, median and interquartile range for continuous variables, differentiating by reference population and treatment group.

In the first analysis a qualitative comparison between the treatment groups will be carried out (healed/not healed) through the test  $\chi^2$  or the exact test of Fisher in the case of counts of less than 5. The results will be presented in contingency tables and bar charts.

A quantitative comparative statistic between treatment groups will then be performed by comparing the percentage reduction in the area of injury, the variation in quality of life level (QoL) and the variation in pain perception (VASS) through Mann-Whitney's nonparametric test.

The choice to perform a non-parametric analysis lies in the low sample size and therefore it is preferred to have more conservative significance values. The results will be presented in tables with median and interquartile interval in the two groups with its p.value and graphically through the box plot.

To analyze the internal and time-related differences between groups, Friedman's non-parametric test for the outcome variables will be performed.

Generalized linear models (GLM) will be used to investigate whether differences between the two groups are influenced in a confusing way by demographic, clinical covariates, pre-treatment measurement, and to measure their impact which will allow us to understand which variables they include on the outcome and will also allow us to analyze the differences between the equal groups of these covariates.

For the comparison about recovery time, since the study is based on the principle of "intention to treat" and therefore there is no caesura, it will be performed by comparing the average recovery times through the non-parametric test of Mann-Whitney.

Then a descriptive statistic will be made through tables with frequencies and percentages, and bar charts of the treatment satisfaction indices in patients and operators. In addition, adverse events in both groups will be described, if present.

Due to the generally asymmetric nature of the cost distribution, the comparison of the costs associated with the two treatment arms, both from the perspective of the SSN and the Company, will be carried out using the non-parametric U test of Mann-Whitney.

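### The safety endpoint is a raw event count, and the protocol does not fix how long healed patients are observed for adverse events

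*Protocol*

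**What the plan says.** **Endpoint and purpose.** Item 8 of Study secondary endpoints is "Security of treatment (number of Adverse Events in the two groups". It serves the aim, under Study Objectives, of showing that EmoLED is "at least as safe in terms of occurrence of adverse events". The Statistical analysis section says only that "adverse events in both groups will be described, if present".

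**Capture.** Measurable parameters lists "Detection of Adverse Events (Annexes B, C". Annex B is the centre's visit form and Annex C the home-care form, completed twice a week. For Annex B, "there is a table for reporting adverse events that will occur during the trial".

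**Follow-up after healing.** The sections differ:
- Measurable parameters, on the photographs, clinical data and pain scores taken at home visits: "These variables will be measured at each visit or until healing".
- Image acquisition: images for 24 weeks, or until healing with a possible confirmation check-up.
- Medical-surgical procedures and study follow up: a wound that heals at home is checked at the centre within a week. Centre check-ups are every 30 days, with no stated stop at healing.
- Registration of clinical data, on the patient's acceptance questionnaire: "last visit, scheduled after 24 weeks, or on the date of recovery".
- Therapy satisfaction questionnaire (Annex F), on the same questionnaire: "scheduled after 24 weeks, or at the control visit 4 weeks from the date of recovery".
- Study primary endpoint, Study design and the quality-of-life form: week 24, with no alternative for healed patients.

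**The concern.** The protocol never states the adverse-event window for a healed patient, and the nearby timings conflict. The endpoint is a number of events with no reference to time observed. Observation may therefore depend on the efficacy outcome.

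If EmoLED speeds healing, as the trial hopes, treated patients could contribute fewer observed weeks and fewer home contacts. Some of any lower event count would then reflect shorter or less frequent observation, yet it could be read as better safety. Events after closure would be least likely to be recorded in the patients who responded best. The Statistics section presents the trial as a proof of concept whose results may inform later studies, so a distorted safety count could be carried forward.

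**Working it through.** **No plan figure to reproduce.** The sample size rests on recruitment capacity, and the protocol gives no adverse-event rate and no expected healing rate by arm. Its durations agree with each other: 20 + 4 = 24 weeks; with the 2-week run-in, 26 weeks; 2 × 20 = 40 treatments.

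**Inputs from the protocol.** There are 20 patients per arm and planned observation is 24 weeks. Let c be the weeks of collection after healing:
- c = 0, from the date of recovery (Registration of clinical data)
- c = 1, the latest confirmation check-up (Medical-surgical procedures and study follow up)
- c = 4, the control visit (Annex F section)
- or follow-up of everyone to week 24

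**Assumptions, not in the protocol.** Healing times T are exponential, with proportion p healed by week 24. The event rate per patient-week is constant, the same in both arms, and unchanged by healing.

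**Formula.** With L = −ln(1 − p)/24, mean observed time per patient is

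E[min(T + c, 24)] = c + (1 − exp(−L(24 − c)))/L.

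Expected events per arm = 20 × weekly rate × mean observed time, so the ratio of expected counts equals the ratio of observed times.

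**Worked case, c = 0.** Control p = 0.30: L = 0.3567/24 = 0.01486, observed time = 0.30/0.01486 = 20.2 weeks. EmoLED p = 0.50: L = 0.6931/24 = 0.02888, observed time = 0.50/0.02888 = 17.3 weeks. Ratio 0.86.

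**Range.** Observed weeks per patient, control v EmoLED (ratio EmoLED/control):

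| Healed by week 24, control / EmoLED | c = 0 | c = 1 | c = 4 | All to week 24 |
|---|---|---|---|---|
| 30% / 50% | 20.2 v 17.3 (0.86) | 20.5 v 17.8 (0.87) | 21.3 v 19.2 (0.90) | 24 v 24 (1.00) |
| 40% / 60% | 18.8 v 15.7 (0.84) | 19.2 v 16.3 (0.85) | 20.3 v 18.0 (0.89) | 24 v 24 (1.00) |
| 50% / 70% | 17.3 v 14.0 (0.81) | 17.8 v 14.6 (0.82) | 19.2 v 16.6 (0.87) | 24 v 24 (1.00) |
| 30% / 70% | 20.2 v 14.0 (0.69) | 20.5 v 14.6 (0.72) | 21.3 v 16.6 (0.78) | 24 v 24 (1.00) |

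The deficit runs from 1 − 0.90 = 10% to 1 − 0.69 = 31%. With 30% healed in both arms, every ratio is 1.00.

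**Speed alone is enough.** Suppose 50% heal in each arm, at week 16 (control) or week 8 (EmoLED). With c = 0: 0.5 × 16 + 0.5 × 24 = 20.0 v 0.5 × 8 + 0.5 × 24 = 16.0, ratio 0.80. With c = 4: 0.5 × 20 + 0.5 × 24 = 22.0 v 0.5 × 12 + 0.5 × 24 = 18.0, ratio 0.82.

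**How often a single trial would show it.** A Poisson simulation (200,000 runs, 30%/50% healing, 0.05 events per patient-week, equal risk) gave:

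| Window | EmoLED count lower | EmoLED count higher |
|---|---|---|
| c = 0 | 0.64 | 0.30 |
| c = 1 | 0.63 | 0.31 |
| c = 4 | 0.60 | 0.34 |
| All to week 24 | 0.47 | 0.47 |

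**The case against.** A reader might infer that adverse-event collection ends at or soon after healing, so that the treated arm is bound to look safer. The protocol does not support that.

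- The until-healing sentence in Measurable parameters concerns photographs, clinical data and pain scores. Adverse-event detection is a separate item with no healing limit.
- The two conflicting dates, at recovery or four weeks later, are for the satisfaction questionnaire and not for a safety cut-off.
- The Annex B table covers events throughout the trial. Observation is 24 weeks, the primary endpoint is read at week 24, quality of life is collected then, and the monthly centre visits have no stated end at healing. Every adverse event must also be reported to the sponsor.
- The analysis is descriptive, so no error rate is affected. Patient-level or per-time summaries can be left to a statistical analysis plan.
- Fewer wound-related events after closure, such as infection, are partly real benefit and not an artefact.

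All of this stands, and it rules out the stronger reading. It does not settle the window. The section on safety follow-up concerns conditions that have already arisen, not how new events are found. Annex B has a place for the observation period after treatment ends, but the protocol does not say how long that period is for a patient who heals early. Even if monthly visits continue to week 24, home visits are tied to dressing changes. If they lapse once the wound has closed, detection falls from twice weekly plus monthly to monthly alone. An analysis plan can add a rate, but it cannot recover events that were never collected.

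**Conclusion.** The point holds as an ambiguity with a predictable direction. The end of observation for healed patients is stated inconsistently, and the safety endpoint is a count that cannot absorb the difference. If collection in practice stops 0-4 weeks after healing, the faster-healing arm would have about 10-31% fewer expected events at equal weekly risk. That range rests wholly on the assumed healing proportions and a constant event rate. The effect is zero if all patients are followed to week 24, or if healing has the same frequency and timing in both arms.

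It is a tendency only: with 20 per arm and 30%/50% healing, the EmoLED count is still the higher one in about 30-34% of simulated trials. If monthly visits do continue for everyone, what remains is less frequent detection after healing, which the protocol gives no means to size. This is a cheap improvement to the safety comparison. It does not bear on the primary efficacy result.

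**What to change.** 1. State that adverse events are collected from randomisation to week 24 in every randomised patient, healed or not, at the monthly centre visits already scheduled. Allow a telephone contact if a healed patient no longer receives home care.
2. Define endpoint 8, by arm, as the number of patients with at least one event and the events per patient-week observed, beside the raw count. The common window matters most: if collection were still cut at healing, a rate would compare different phases of the wound's course in the two arms.
3. Reconcile Medical-surgical procedures and study follow up, Measurable parameters, Registration of clinical data, the Annex F section and Image acquisition, so that each gives the same end of follow-up for a healed patient. Keep data items that may stop at healing apart from adverse events, which should not.

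The cost is protocol wording and a few extra contacts for healed patients.
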